7.4 Vital Sign Measurements

In the clinic, measurements of the vital signs described below will be made by a trained and authorized person. These will be made at Baseline (if not available from within the prior 42 days) and every subsequent visit thereafter (or upon early termination), including the 4-week post-treatment follow-up visit if applicable.

7.4.1 Blood Pressure and Pulse

Blood pressure and pulse should be measured with the subject in a seated position for at least 5 minutes. A manual or automated sphygmomanometer will be used to measure systolic and diastolic blood pressure, with results recorded in mmHg. Pulse rate will be measured in the radial artery for 60 seconds and will be recorded as beats/minute. If possible, blood pressure and pulse rate preferably should be measured in the same arm at each visit.

7.4.2 Temperature and Respiratory Rate

Temperature and respiratory rate will be measured for evaluation in the assessment for signs and symptoms indicative of potential serotonin toxicity. Oral (sublingual) temperature measurements are preferable; aural temperature is an acceptable alternative (this alternate means of measuring temperature is to be recorded in the eCRF).

7.4.3 Weight

Body weight will be recorded at Baseline (if not available from within the prior 42 days) and every subsequent visit thereafter (or upon early termination), including the 4-week post-treatment follow-up visit if applicable. Weight will be measured while the subject is clothed with shoes off and recorded in kilograms (kg).

7.5 Electrocardiography

A 12-lead ECG of at least 10 seconds in duration will be obtained in triplicate (taken within a period of 5 minutes) at Baseline (if not available from within the prior 42 days) and approximately every 6 months thereafter (or upon early termination), including the 4-week post-treatment follow-up visit if applicable. Recordings will be evaluated by a centralized ECG reading facility. Interval data (including QT and corrected QT intervals), ventricular rate, and overall interpretation are to be reported for every ECG. The interval data and ventricular rate are to be noted in the eCRF as averages of the three readings (with the exception of values that are not evaluable and reported as zero, in which case the average will exclude this zero value and note in the eCRF the average of values > 0).

A local cardiology consult should be sought if the investigator deems it necessary. For evaluation of subjects with left bundle branch block, a cardiology consult is strongly recommended.

7.6 Physical and Neurological Examinations

Targeted examinations (as described below) are to be performed at Baseline (if not available from within the prior 42 days) and every subsequent visit thereafter (or upon early termination), including the 4-week post-treatment follow-up visit if applicable. In the event of an abnormality, subjects should continue to be followed until resolution or stabilization.

The targeted examinations are to be focused on, but not limited to, evaluating subjects for potential serotonin toxicity (see Section 7.1.3.2 for guidance on assessment) and also as clinically indicated (*e.g.*, targeted to any changes in medical history, in the event of an AE that requires such follow up, or any reported change in the subject's physical condition). At a minimum (in addition to assessments for serotonin toxicity), they are to include evaluation of deep tendon reflexes, clonus, and muscle rigidity; size and reactivity of pupils; dryness of oral mucosa; intensity of bowel sounds; skin color; and presence or absence of diaphoresis.

Additional targeted examinations may be performed as clinically indicated (*e.g.*, in the event of an AE that requires such follow up or any reported change in the subject's physical condition).

Findings will be documented in the subject's medical record and in the eCRF.

8 OTHER ASSESSMENTS

8.1 Mini-Mental State Examination (MMSE)

The MMSE (Folstein *et al.*, 1975) was originally developed to differentiate between psychiatric patients with functional and organic conditions, to quantify the level of cognitive impairment, and to monitor changes over time. The MMSE subsequently has become a widely used and extensively validated cognitive test demonstrating satisfactory reliability, validity, and change sensitivity under a wide variety of conditions (Tombaugh and McIntyre, 1992).

Over a 12-month period, Alzheimer's disease patients might typically show a decline in MMSE score of 2-4 points (Schneider, 2001).

The utility of the MMSE as a means of assessing treatment response in Alzheimer's disease has been questioned (Bowie *et al.*, 1999), but its status as a clinical outcome measure has been supported by the UK National Institute for Clinical Excellence guidance (NICE, 2001). Furthermore, the MMSE has demonstrated an ability to detect change in clinical studies with AChEIs (Birks and Harvey, 2004).

In an epidemiological study (Mukaetova-Ladinska *et al.*, 2000), pre-mortem MMSE scores have been correlated with post-mortem Braak stage (based on the spread of tau pathology through the brain). MMSE is also sensitive to decline in bvFTD (Knopman *et al.*, 2008).

The MMSE will be performed at Baseline (if not available from within the prior 42 days) and approximately every 6 months thereafter (or upon early termination) and at the 4-week follow-up visit (if applicable) by raters deemed appropriate and delegated by the principal investigator. For each individual subject, the MMSE questionnaire to be utilized in this study will be the same version utilized for the subject in the respective originating double-blind study (to maintain longitudinal consistency per subject). The MMSE scores will be used to inform the evaluation for possible serotonin toxicity (to be included in the targeted physical and neurological examinations).

8.2 Resource Utilization in Dementia Questionnaire (RUD Lite)

The RUD was developed as a comprehensive instrument to measure resource use by patients in a clinical trial setting, which in a further step can be calculated into costs (Wimo *et al.*, 1998; Wimo *et al.*, 2003; Jonsson, 2007). The RUD Lite is a shorter version of the RUD (Wimo and Winblad, 2003). The RUD and RUD Lite assess both formal and informal resource use, making it possible to calculate costs from a societal perspective. The RUD is administered as an interview with the caregiver. The validity and reliability of the RUD instrument has been investigated both in residential care and community care settings by comparing responses to the RUD questions with actual observations of care-giving time (Jonsson, 2007; Wimo and Nordberg, 2007).

The following dimensions are captured on the subjects' part: accommodation/long term care, respite care, hospital care, social service, and home nursing care. In addition, the following aspects are covered from the caregiver perspective: caregiving time for the subject and work status.

The RUD Lite will be performed at Baseline (if not available from within the prior 42 days) and approximately every 6 months thereafter (or upon early termination).

8.3 EuroQol – 5 Dimension – 5 Level Instrument (EQ-5D-5L)

The EQ-5D-5L is a standardized instrument developed by the EuroQol Group to describe and value health-related quality of life. It has been utilized in a global Phase 3 study in patients with AD (using the EQ-5D Proxy version completed by caregivers)⁶. The

⁶ <https://clinicaltrials.gov/ct2/show/NCT00762411>

instrument comprises the following five dimensions: mobility, self-care, usual activities, pain/discomfort and anxiety/depression. Each dimension is rated by the subject and caregiver on a 5-point scale as having “no problems” (a score of “1”), “slight problems” (a score of “2”), “moderate problems” (a score of “3”), “severe problems” (a score of “4”), and “extreme problems” (a score of “5”) based on descriptive examples; the scores are not intended to be summed. Present overall state of health is also to be rated on a vertical visual analogue scale (approximately 20 cm in length) from 0 to 100 (the higher the number the better the quality of life).

The EQ-5D-5L will be performed at Baseline and approximately every 6 months thereafter (or upon early termination). There will be two applications of the self-reported EQ-5D-5L at each visit: one version will be completed by the subject and a second copy of this version will be completed by the caregiver.

For application to the subject, the rater should explain to the subject what is required and how to complete the scale. If the rater deems that the subject can then complete without further assistance, the subject should then proceed to complete the scale without further assistance from the rater. If a subject cannot complete the scale, the rater will be permitted to read the questions and options for response and report the subject’s responses. There should be no assistance from the caregiver.

For application to the caregiver on behalf of the subject, the rater should guide the caregiver in completing the scale as though the caregiver is responding for the subject, giving what the caregiver believes to be an accurate response to each question. If the caregiver cannot complete the scale, the rater will be permitted to read the questions and options for response and report the caregiver’s responses.

It is important to ensure that the subject and caregiver each complete the EQ-5D-5L independently (although the subject and caregiver may each be assisted by a rater), with the assessments not influenced by knowledge of the other’s responses. If independence cannot be assured, the order of administration of the EQ-5D-5L is subject first, followed by the caregiver.

9 STATISTICAL PLAN

A statistical analysis plan (SAP) will be written and finalized prior to database lock. A detailed description of the planned statistical analyses will be provided in the SAP; changes from analyses described in this protocol will be documented in the final study report. The database will be locked after review of data is complete, all queries are resolved, and all decisions made about the inclusion or exclusion of any spurious data and the handling of unused or missing data.

For purposes of safety reporting and regulatory submissions, one or more interim reports may be prepared prior to study termination.

9.1 Efficacy Endpoints

Not applicable to this open-label extension study.

9.2 Sample Size Calculations

Not applicable to this open-label extension study.

9.3 Statistical Analysis

9.3.1 Analysis Populations

The Safety Population will include all subjects who take at least one dose of study drug. Subjects dispensed study medication who subsequently are lost to follow up without any contact are not included in the Safety Population but will be included in the study disposition tabulation and listings. With the exception of study disposition, all tables and listings will be generated on the basis of the Safety Population.

9.3.2 General Considerations

Results will be summarized descriptively; no inferential statistics are planned. Tabulations will be on the basis of all subjects pooled and also with subjects categorized separately by diagnosis and also by study of original participation. Data from the prior study will be mapped into the open-label database.

For purposes of calculations of change from baseline, Baseline (Visit 1) for the open-label study will be used. Depending on the parameter, the data may have been acquired during the double-blind study of prior participation.

For purposes of data tabulations, target visit windows will be assigned in the SAP.

Listings of by-subject data will be organized by subject number.

9.3.3 Health Economic Analysis

A summary of the planned analyses is provided below; a detailed description of the planned analyses, as well as intended sensitivity analyses, will be provided in the SAP.

In order to investigate the pharmacoeconomic impact of LMTM, two approaches will be used:

- a cost consequence analysis (CCA), and
- a cost utility analysis (CUA).

With a cost consequence analysis, a broad set of relevant outcomes (here the primary and secondary outcomes) can be tabulated and discussed in relation to costs (Mauskopf *et al.*, 1998). Costs and outcomes are presented separately.

In the cost utility analysis, the incremental cost effectiveness ratio (ICER) is analyzed. As an outcome, the gained quality adjusted life years (QALY) derived from the EQ5D instrument will be used.

Both pharmacoeconomic approaches mentioned above include a risk of getting non-significant effects regarding costs, as clinical trials evaluating efficacy are typically

underpowered with respect to pharmacoeconomic results and long-term effects cannot be assessed due to time constraints in the clinical trials. Therefore, a modeling approach will complement the analysis.

9.3.3.1 *Resource Use*

The Resource Utilization in Dementia instrument (RUD) is a comprehensive and validated instrument collecting data on resource use in trials, with the aim to calculate costs from a societal viewpoint. The RUD Lite questionnaire, a short version of RUD mainly discarding the resource use by the caregivers, is employed in this study. All subjects for whom RUD Lite data was collected for at least one time point will be included in the summaries.

Together with costs of institutional care, the value of informal care is the heaviest cost driver in dementia care. Three components of caregiver time will be included in the analysis:

- time spent on toilet visits, eating, dressing, grooming, walking and bathing;
- time spent on shopping, food preparation, housekeeping, laundry, transportation, taking medication and managing financial matters; and
- time spent on supervising the subject.

Each component of caregiver time will be calculated as the hours of care on a typical day multiplied by days spent on providing these services. The caregiver time will be summarized for each treatment group by visit and with AChEI and/or memantine status at randomization, severity, and geographic region.

Caregiver work status, whether the subject was admitted to a hospital, whether the subject received services in a hospital emergency room, whether the subject visited any health care professional, and whether the subject received any nursing services will be summarized likewise.

Caregiver relationship with subject and the subject's living accommodations will be summarized descriptively.

9.3.3.2 *Unit Costs*

Costs will be calculated as the multiplication of the amount of units of resource use and the unit cost for this particular resource. Unit costs for each unit will be collected for each country (if unit cost data are not available for each trial country, then unit cost data for the dominant country only will be used). An average wage will be used as a proxy for the opportunity cost of informal care. Caregiver time for retired carers will be given a value of 35% of caregivers of working age (Johannesson *et al.*, 1991).

9.3.3.3 *Statistical Analysis*

In order to statistically support the descriptive analysis, regression models will be employed. Generalized linear models assuming gamma distributed dependent variables will be used accounting for the skewness of resource use and cost data. Bootstrapping methods will complement the analysis by providing estimates for the confidence intervals (Ramsey *et al.*, 2005) in the univariate analyses.

If there is a substantial amount of missing data on resource use (> 20%), multiple imputation approaches will be tested.

9.3.3.4 *Economic Modelling*

As the long term cost-effectiveness of LMTM beyond the trial periods is of great interest, economic evaluations based on various modeling techniques will be used. These models most often have a CUA design in which the relation between costs and outcomes is expressed as the ICER. The QALY concept is the most frequently used outcome. External data for disease progression and mortality as well as data on resource use and costs beyond the trial period are used as inputs. From the trial, data on efficacy are used as an empirical core for the model. Within trial data on resource use and costs as well as the EQ5D data calibrates the external sources in the model. Often-used modeling techniques such as Markov models (Sonnenberg and Leventhal in Wimo *et al.*, 1998) and Discrete Event Simulations (DES) (Guo *et al.*, 2014) will be tested.

9.4 **Baseline Characteristics and Concomitant Medications**

Tabular summaries of demographics and baseline characteristics will be prepared based on data collected at the Baseline visit for the original study of participation and at baseline for the open-label extension study. Tabular summaries of concomitant medication use (ongoing at start of study and newly initiated) will be restricted to the open-label extension study. All data, including study eligibility, will be listed.

Concomitant medications and recently used medications (anti-dementia and psychiatric drugs used within the prior 3 months) will be coded using the most current version of the World Health Organization (WHO) drug dictionary. Tabulations will be prepared of all drugs used concomitantly (relative to the first dose of study drug in the open-label extension study) based on WHO Anatomical Therapeutic Classification (ATC) level 1 term, ATC level 3 term, and Preferred Term (generic name) with frequency and percentage of subjects using each concomitant medication. Concomitant medications are to be listed with these elements as well as the verbatim drug name.

9.5 **Study Drug Exposure**

Total duration of exposure and mean daily dose per subject over the treatment period in the open-label study will be summarized descriptively. The proportion of subjects with dose interruptions and/or dose reductions will be summarized descriptively.

9.6 **Safety Analysis**

The analysis of safety will include summaries of AEs, laboratory tests, vital signs, ECGs, and physical and neurological examinations (including serotonin toxicity assessments).

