The majority of the safety assessments (described further in Section 7) will be repeated at each visit, *i.e.*, approximately 2 weeks post-Baseline and at visits occurring approximately every 3 months (13 weeks) relative to Baseline. These assessments include adverse event and concomitant medication recording, seated blood pressure and pulse, body weight, clinical laboratory testing (*e.g.*, hematology and serum chemistry panels), serum pregnancy testing in women of childbearing potential, and targeted physical and neurological examinations. The 12-lead ECGs will be obtained approximately every 6 months (26 weeks) relative to Baseline. Throughout the assessments for safety, the investigator is to be cognizant of the potential for serotonin toxicity, taking the MMSE into consideration as well.

The EQ-5D-5L, applied to the subject and to the caregiver on behalf of the subject, will be evaluated at Baseline (as it is not used in the Phase 3 studies of prior participation). The RUD-Lite will be also be evaluated at Baseline if not available from within the prior 42 days. These evaluations will be repeated approximately every 6 months (26 weeks) relative to Baseline.

The same aforementioned 13-week and 26-week schedules of in-clinic assessments will be maintained for continued treatment beyond the first 12 months (if there is re-consent at Visit 6), with no requirement for the Week 2 visit or Week 6 telephone contact in the second or any subsequent year of participation. Continued treatment will be restricted to those subjects for whom continued benefit is expected by the investigator to outweigh risk and informed consent is provided.

For subjects who do not re-enroll for a subsequent extension of treatment, identified end of treatment evaluations will be performed at the final on-treatment visit (*e.g.*, Visit 6). If a subject discontinues prematurely, an early termination visit should be conducted at which time all assessments identified for Visit 6 should be performed.

Post-treatment safety assessments will be conducted at a follow-up visit, to be scheduled to occur approximately 4 weeks after the last dose of study drug for all subjects who cease to take LMTM (regardless of the reason for discontinuation).

A schedule of assessments is shown in Table 4-1. Assessments are listed by visit in Appendix A: Assessments by Visit.

Table 4-1 Schedule of Assessments

Visit Name	Baseline ^a						First 12 Month Open-Label Extension ^b						Follow-up ^c

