4.5 Assignment of Treatment

This is not applicable to this open-label study as all subjects will receive LMTM. Treatment assignment from the prior double-blind clinical study will be recorded in listings; however, this information will remain unknown to the subject and caregiver as well as to the investigator and study site personnel until the blind for the respective double-blind trial has been broken.

Subjects will be assigned a study identification number with the first three digits for the study (020), the next two letters for the country, the next three digits for the site, and the last two digits for the sequential order of enrollment at a given site.

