### 8.2 EQ-5D-5L

The EQ-5D-5L is a standardized instrument developed by the EuroQol Group to describe and value health-related quality of life. The EQ-5D-5L will be performed at baseline and approximately every 6 months thereafter (or upon early termination). There will be two

applications of the self-reported EQ-5D-5L at each visit: one version will be completed by the subject and a second copy of this version will be completed by the caregiver.

The instrument comprises the following five dimensions: mobility, self-care, usual activities, pain/discomfort and anxiety/depression. Each dimension is rated by the subject and caregiver on a 5-point scale as having “no problems” (a score of “1”), “slight problems” (a score of “2”), “moderate problems” (a score of “3”), “severe problems” (a score of “4”), and “extreme problems” (a score of “5”) based on descriptive examples; the scores are not intended to be summed. Present overall state of health is also to be rated on a vertical visual analogue scale (approximately 20 cm in length) from 0 to 100 (the higher the number the better the quality of life). Each of the five dimensions as well as the overall state of health will be summarized descriptively by visit. Following the 24-Aug-2015 CRF migration, the original EQ-5D-5L eCRF was inactivated and the EQ-5D-5L Patient Rated and EQ-5D-5L Caregiver Rated eCRFs were activated. For subjects under version protocol version 1.1, only the EQ-5D-5L was applied to the subject, who should receive no help from the caregiver. For subjects under protocol version 2.1 or later versions, EQ-5D-5L is to be applied separately to both subject and caregiver. For the purposes of this summary, data obtained from the original EQ-5D-5L eCRF prior to the 24-Aug-2015 CRF migration and data obtained from the EQ-5D-5L Patient Rated eCRF after the 24-Aug-2015 CRF migration will be used.

The EQ-5D-5L health economic and economic modelling, and additional sensitivity analyses will be addressed in a separate external SAP.

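### Protocol 9.3.3 plans a within-study ICER and QALY gain, but 020 is single-arm and no comparator is named, so neither quantity is identified from 020 data

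*Protocol*

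**What the plan says.** Protocol Section 9.3.3 sets out a cost consequence analysis and a cost utility analysis. For the second, "In the cost utility analysis, the incremental cost effectiveness ratio (ICER) is analyzed", and "As an outcome, the gained quality adjusted life years (QALY) derived from the EQ5D instrument will be used". Modelling is described as a complement to these two analyses, so the cost utility analysis stands as a planned analysis in its own right.

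Section 9.3.3.1 adds that "The caregiver time will be summarized for each treatment group by visit", with a further split by AChEI/memantine status at randomization. Section 9.3.3.4 plans Markov or discrete-event models and says: "From the trial, data on efficacy are used as an empirical core for the model".

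Elsewhere the protocol describes a different kind of study. On assignment of treatment, Section 4.5 says: "This is not applicable to this open-label study as all subjects will receive LMTM". Section 9.1, on efficacy endpoints, reads: "Not applicable to this open-label extension study". Section 2 drops the formal efficacy scales because the study is open-label. Section 4.4 says that the EQ-5D-5L "will be evaluated at Baseline (as it is not used in the Phase 3 studies of prior participation"), and Appendix A says the same of the prior double-blind studies generally.

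The SAP summarises EQ-5D-5L and RUD Lite descriptively (Sections 8.2 and 8.3). It then defers the rest: "The EQ-5D-5L health economic and economic modelling, and additional sensitivity analyses will be addressed in a separate external SAP". Section 8.3 does the same for RUD Lite unit costs and modelling.

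**The concern.** An ICER needs costs and QALYs under two strategies, and 020 observes one. The section reads as if written for a controlled efficacy trial. It refers to treatment groups, to primary and secondary outcomes, and to trial efficacy data at the centre of the model, none of which 020 has in the ordinary sense. A programmer given Section 9.3.3 could not execute the cost utility analysis without choosing a comparator.

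The risk is that the gap is filled by change from Baseline, or by an external control chosen later, and the result is presented as a protocol-specified cost-effectiveness estimate. In a progressive disease, with continuation decided partly on judged benefit, such a figure would not have a causal reading as the effect of LMTM.

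**Working it through.** The plan states no ICER, QALY, power or sample-size figure for this analysis, so there is nothing to reproduce. The check is structural, with one illustration on assumed values.

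**1. Definition.** ICER = (C1 - C0) / (Q1 - Q0), where 1 is LMTM and 0 is the comparator. 020 can inform C1 and Q1. C0 and Q0 need a comparator, and none is named.

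**2. Identifiability.** Regress cost or QALY on an intercept and a treatment indicator. With everyone treated, both columns are all ones. Taking 1,050 subjects, the lower end of the protocol's anticipated enrolment, the design matrix has rank 1 for 2 parameters. The treatment contrast cannot be estimated, and more subjects would not help. The gamma regressions and bootstrap intervals of Section 9.3.3.3 do not change this.

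**3. Illustration.** Assumed, not from the documents: observed one-year QALY 0.70 and incremental cost 10,000. Then ICER = 10,000 / (0.70 - Q0).

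| Unobserved Q0 | 0.70 - Q0 | ICER |
|---|---|---|
| 0.60 | 0.10 | 100,000 |
| 0.65 | 0.05 | 200,000 |
| 0.69 | 0.01 | 1,000,000 |
| 0.70 | 0.00 | undefined |
| 0.71 | -0.01 | -1,000,000 |
| 0.75 | -0.05 | -200,000 |
| 0.80 | -0.10 | -100,000 |

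Size and sign depend wholly on Q0. The illustration is generous, because it treats the incremental cost as known when C0 is equally unobserved.

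**4. Could change from Baseline stand in for the contrast?** Entry requires completing the prior study and an investigator who expects the subject to keep benefiting (Section 4.2). Treatment is renewed yearly on the same judgment (Section 4.4), and lack of efficacy, including progression, is a listed reason for stopping (Section 5.3). Section 8.1 cites a typical AD decline of 2-4 MMSE points over 12 months. Change within subjects therefore mixes drug, disease course and selection. The documents give no mapping from MMSE to EQ-5D or cost, so the shares cannot be computed. Contrasts by dose taken fail for a similar reason: Section 6.2.2 lets dose follow judged benefit and tolerability.

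**5. Could MMSE supply the effect?** SAP Section 8.1 models MMSE, but with treatment allocation pooled. It gives no treatment contrast.

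**The case against.** The strongest reply is that 020 does carry some comparative information and that the plan does not rely on 020 alone.

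- **Prior arms are known.** Prior assignment is recorded (Protocol 4.5, SAP 3.2), and SAP Table 14.3.2.1.3.3 tabulates adverse events by it. A contrast of early with delayed start is therefore computable. This stands, so it would be wrong to infer that the design can yield no incremental quantity at all. But no economic contrast by prior arm is planned, it would cover only completers who chose to enrol, and it would have no EQ-5D from the double-blind period. It is also a different question from LMTM against no LMTM. RUD Lite may be carried over from the prior study (Protocol 4.4 and 8.2), so the missing prior data concern QALYs rather than resource use.
- **The model uses outside data.** Section 9.3.3.4 takes progression, mortality and later costs from external sources and uses 020 cost and EQ-5D data for calibration, which is reasonable. It also speaks of trial periods in the plural, so its efficacy input may not mean 020 alone. This makes a programme-level ICER possible, but the text still names neither the comparator nor the source of the effect.
- **The SAP produces no ICER.** Its table list has only descriptive RUD Lite and EQ-5D output. A reader might infer that a before-after ICER will be reported; the visible SAP does not support that, and the external SAP may name a comparator. The protocol's commitment nevertheless remains uncorrected.
- **The wording may have a referent.** SAP 8.1 uses AChEI/memantine use as randomised in the prior study, so the randomization phrase in Section 9.3.3.1 probably means that. It needs clarifying, not deleting.

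**Conclusion.** The point holds for the within-study cost utility analysis in Section 9.3.3. From 020 data, the incremental cost and QALY of LMTM against no LMTM are not identified, and neither document names a comparator. This is an error in what is planned rather than a missing detail.

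The size is structural: 020 contributes no information on the contrast, whatever its enrolment. The ICER values tabulated above rest on assumed inputs and show sensitivity only. A reader might also infer that before-after change is mainly disease course and drop-out. The documents make confounding plausible but do not quantify it, and the MMSE figure is for AD only.

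The conclusion assumes that the within-study analysis means 020 and that the target is LMTM against no LMTM. It does not extend to a model drawing its effect from elsewhere. Cost-effectiveness is not among the objectives, which are access and long-term safety and tolerability, so this warrants a text correction and does not threaten the study's main purpose.

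**What to change.** - **Section 9.3.3:** remove the within-020 ICER and QALY gain. State that 020 provides descriptive resource use, cost and EQ-5D by visit, as SAP 8.2 and 8.3 already do for resource use and EQ-5D.
- **Section 9.3.3.4:** replace the sentence "From the trial, data on efficacy are used as an empirical core for the model". Say instead that any modelled ICER takes its incremental effect from a named controlled source: the randomised double-blind studies, or a justified external comparator with a stated adjustment method. 020 supplies cost and utility inputs only, not an uncontrolled before-after change. If the double-blind studies are used, say how their clinical effects are converted to utilities, since they have no EQ-5D.
- **Section 9.3.3.1:** replace the reference to treatment groups with the groups actually used (diagnosis or prior-study arm), and specify that randomization means randomization in the prior study.
- **External SAP:** carry the same comparator, effect source and adjustment method into it.

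The cost is wording in the protocol and the external SAP. The sponsor gives up a within-020 cost-effectiveness estimate that the data could not support. Data collection and safety outputs are unchanged.
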